Long-term outcomes of successful chronic total occlusion percutaneous coronary interventions using the antegrade and retrograde dissection and re-entry approach.

(LOTUS-ADR/RDR)

Protocol

Sponsored by: Department of Cardiology, Xi'jing Hospital.

The Fourth Military Medical University (FMMU)

Approved by: Ethics Committee, Xi'jing Hospital. FMMU

Approved Ethical Number: KY20172019-1

Approved date: 2017.03.15

Last Update: 2018.11.20

Study Time: 2018.12.01- 2019.12.30

Versions: V2.0

ABSTRACT

BACKGROUND: Chronic total occlusion (CTO) angioplasty is one of the most challenging procedures remaining for the interventional operator. Today, with contemporary CTO negotiation available strategies and significant operator expertise, the literature reports a 50-95% success rate for recanalizing CTOs. But PCIs of CTO lesions still carry a high rate of in-stent restenosis (ISR). Because previous reports have not specifically compare contemporary antegrade and retrograde dissection and re-entry dissection (ADR/RDR) technique on the long-term impact of ISR, so the investigators focused on the objective.

OBJECTIVES: This study hope to evaluate the frequency of angiographic ISR and further elucidate some ISR related higher risk factors among CTO PCI patients in intimal stent group using antegrade or retrograde wire escalation (AWE/RWE) techniques and sub-intimal stent group using contemporary antegrade or retrograde dissection and re-entry (ADR and/or RDR).

METHODS: A total of 300 consecutive selected patients with CTO lesion who will undergo successful revascularization by AWE/RWE and ADR/RDR techniques treatment will be enrolled in this prospective multicenter registry from December 1 2018 to December 31 2019. The primary study endpoint of the protocol is the binary in-stent restenosis of CTO vessels at angiographic follow-up about 13 months. The secondary endpoints are: 1) CTO technique and procedure success rate; and 2) in-hospital and 30 days MACE (Cardiac death, acute myocardial infarction, urgent repeat target vessel revascularization with either pericardiocentesis or surgery and stroke and stent thrombosis and stroke); 6months and 1-year and 2-year MACE including death, MI, and target CTO vessel revascularization and stroke ; and 3) Restenosis scores (R-scores) of related risk factors.

CONCLUSIONS: This study expect to identify long-term effect of ADR and RDR methods on the ISR incidence and predictors.

INTRODUCTION

Chronic total occlusion (CTO) angioplasty is encountered in 18.4% to 52% of patients with coronary artery disease (CAD) undergoing coronary angiography¹⁻⁴. Observational studies suggest that successful CTO PCI can provide significant clinical benefit to patients, including symptom relief, improved left ventricular function, reduced risk of arrhythmias, and better tolerance of an acute coronary syndrome⁵. CTO is considered one of the most difficult lesion types to treat. With the development of new techniques and dedicated devices, procedural success rates for CTO recanalization have vary between 60% and 90% in recent years⁶⁻¹⁰.

However, CTO lesions have a 1.4- to 5-fold higher rate high risk of in-stent restenosis (ISR), compared with non-occlusive stenosis¹¹⁻¹⁶. ISR, induced by neointimal hyperplasia, is a long-recognized, chronic complication following PCI. Previous studies have reported clinical or lesion-related characteristics (i.e., complex lesion morphology or comorbidities, such as diabetes mellitus)^{17, 18} and calcification and CTO length are known as ISR predictors¹⁹. Whereas Valenti et al. reported that specific techniques (the subintimal tracking and re-entry technique (STAR) was associated with ISR¹¹.

The STAR technique was the first reported antegradesubintimal dissection and reentrymethod to re-open occluded arteries^{20,21}. Although this technique has some limitations, notably the inability to control the reentry point in the distal lumen, it did effectively demonstrate that blunt dissection through the subintimal space could rapidly and safely traverse even very long, tortuous, and calcified occluded segments without vessel perforation²⁰⁻²⁴. This demonstration provided the confidence to further explore the use of the subintimal space for therapeutic purposes²³. STAR was integrated into a retrograde approach (e.g. Controlled Antegrade and Retrograde subintimal Tracking (CART))²⁵⁻²⁷, and a dedicated antegradedissection and re-entry system (CrossBoss™ Catheter and Stingray™ System)²⁸. As a result of these advances and greater operator experience, success rates of CTO PCI have increased²⁹.

There have been concerns raised that the high restenosis rate after STAR³⁰⁻³³ may

be a direct consequence of subintimal stenting. If the cause of the high incidence of restenosis is, in fact, due to use of the subintimal space, newer CTO techniques, which are based on controlled subintimal dissection and reentry methods, also would be expected to be associated with this adverse outcome²⁵⁻²⁸ Now there are only limited data about procedural success of ADR and RDR and retrograde techniques have been demonstrated and the use of subintimal stenting did not adversely impact outcomes^{34, 35}. While prospective studies with longer follow-up are needed to assess the long-term safety and efficacy of sub-intimal stenting.

The purpose of the study was therefore to examine the longer-term outcomes of patient who underwent successful CTO PCI in our program, compare the effect of ADR/RDR on outcomes with everolimus-eluting stents (EES) and assess predictors of long-term events.

METHODS

1. Trial overview and study population.

① This clinical trial is a prospective, exploratory, nonrandomized, multicenter trial evaluating the frequency of angiographic restenosis and clinical outcomes among patients undergoing CTO PCI in intimal stent group using antegrade or retrograde wire escalation (AWE/RWE) techniques and sub-intimal stent group using contemporary antegrade or retrograde dissection and re-entry (ADR or RDR) with everolimus-eluting stents (XIENCE Coronary Stent).

② According to high patient's volume registry studies in CTO lesions, the patients percentage of ADR or RDR strategy application was just only 20-25%³⁶⁻³⁷. If to get 60 patients for ADR or RDR strategies, the minimum CTO number are 300 patients. So in our registry study, 300 CTO cases, to which PCI will be attempted, are prospectively enrolled from December 1 2018 to December 31 2019 in the CTO registries of ten centers. The study was approved by the institutional review board at each site. For patients with multiple treated CTO, only the first CTO attempted was considered for the analysis.

③ Exclusions included age <18-years-old or >85-years-old, left ventricular ejection

fraction $\leq 30\%$, allergy to medications (antiplatelet drugs, heparin, metal alloys, or contrast agents), a planned surgery within 6 months of PCI or planned thrombolysis, pregnant, a life expectancy of <6 months.

④ Patients will sign written informed consent for long-term telephone FU before the interventional procedure. The patients will be followed by a clinical visit or by a telephone interview for 30 day, 6 months and 12 months and 24 months post-procedure for assessment of adverse events. All patients with successful CTO PCI and without moderate or severe renal insufficiency will be scheduled for angiographic follow-up at 13 months. Compared with CTA, coronary angiography to evaluate restenosis is appropriate in all patients especially for severe coronary heart diseases patients with atrial fibrillation and ventricular arrhythmia. It could provide accurate information about mild-severe angulation lesion and the stent straits like total stent length. Procedural and outcome data collection will be collected and entered by operators entered into a dedicated database.

⑤ The study will be performed in accordance with the Declaration of FMMU.

2. Study endpoints and definitions

① The primary study endpoint of the protocol is the binary in-stent restenosis of CTO vessels at the scheduled angiographic follow-up at 13 months. The secondary endpoints are: 1) CTO technique and procedure success rate; and 2) in-hospital and 30 days MACE (Cardiac death, acute myocardial infarction, urgent repeat target vessel revascularization with either pericardiocentesis or surgery and stroke and stent thrombosis and stroke); 6 months and 1-year and 2-year MACE including death, MI, and target CTO vessel revascularization and stroke ; and 3) Restenosis scores (R-scores) of related risk factors.

② Coronary CTOs will be defined as angiographic evidence of total occlusions with TIMI (Thrombolysis In Myocardial Infarction) flow grade 0 and estimated durations of at least 3 months. Estimation of the occlusion duration is based on first onset of anginal symptoms, prior history of myocardial infarction in the target vessel territory, or comparison with a prior angiogram.

③ Procedural success will be defined as angiographic success (final residual stenosis $<30\%$ by visual estimation and TIMI flow grade 3 after CTO recanalization).

④ Clinical success will be defined as a procedural success without In-hospital MACCEs. In-hospital MACCEs is defined as the composite of non-Q-wave and Q-wave myocardial infarction (MI), recurrent angina requiring urgent repeat revascularization with PCI or coronary bypass surgery, stroke, and death. Non-Q-wave MI is defined as creatine kinase-MB enzyme elevation >3 times the upper limit of normal. When new pathological Q waves, in addition to enzyme elevation, will be observed on the electrocardiogram, the event is defined as a Q-wave MI. In all patients, creatine kinase and creatine kinase-MB is evaluated 6 h after the procedure and until their normalization if levels is abnormal.

⑤ Lesion complexity will be judged using the J-CTO (Multicenter CTO Registry in Japan) score (0 ¼ easy, 1 ¼ intermediate, 2 ¼ difficult, 3 ¼ very difficult) (20) and calculated by allocating 1 point each for: non-tapered proximal cap (ie, blunt or ambiguous), any calcification, any tortuosity, occlusion length >20 mm and any prior unsuccessful attempt. J-CTO score of ≥ 2 was defined as complex.

⑥ CTO proximal cap location is defined according to American Heart Association (AHA) classification and additionally coded as either ostial or non-ostial and proximal (left main, proximal left anterior descending, proximal circumflex or proximal right coronary artery) or distal (all other sites). Cap morphology is coded as blunt or tapered, or as ambiguous when there is lack of clarity over the origin of the ongoing vessel. Calcification within the CTO is coded as none visible, mild (spots only), moderate (<50% of vessel circumference) or severe (>50% of vessel circumference). Tortuosity is assessed at baseline or after subsequent equipment passage and coded as straight (no bend or <45° single bend), slight (>45° single bend), moderate (2 bends >45° or 1 bend >90°) or severe (2 bends >90° or 1 bend >120°).

Disease proximal and distal to the CTO is classified as absent, mild, moderate or severe. Proximal or distal cap side branch is considered present if occurring ≤ 3 mm from the respective CTO cap. Occlusion length is estimated by dual injection, or from apparent length after guidewire crossing. Collaterals are classified according to Cohen and Rentrop and deemed interventional if, on angiographic inspection, are thought amenable to crossing by a guidewire and a microcatheter by the operator.

⑦ All deaths are considered cardiac unless otherwise documented. Stent thrombosis is defined according to the Academic Research Consortium criteria (13). Reocclusion is defined as a TIMI flow grade of 0 to 1 in the target CTO vessel, where restenosis is defined as > 50% luminal narrowing at the segment site, including the stent and 5 mm proximal and distal to the stent edges. Target lesion revascularization (TLR) is defined as any repeat PCI or coronary artery bypass graft surgery of the target lesion that includes 5 mm proximal and distal to the stented vessel segment.

⑧ A procedure is considered retrograde if an attempt is made to cross the lesion through a collateral vessel supplying the target vessel distal to the lesion. Complex lesions with unclear location of the proximal cap or with poor distal target are initially attempted by the retrograde approach. In those cases, after positioning of a microcatheter at the distal CTO cap, a true-to-true retrograde lumen crossing technique is first attempted for shorter lesions (<20 mm). When entering in the subintimal space or with longer lesions, knuckled wires are used to reach the proximal cap, followed most often by reverse-controlled anterograde and retrograde re-entry techniques.

⑨ A procedure is considered antegrade if no retrograde crossing attempts are made. An antegrade approach is initially attempted for short lesions (<20 mm) with clear proximal cap location and good distal vessel target using a wiring strategy. Anterograde dissection/re-entry using dedicated devices (CrossBoss and Stingray catheters) is, however, preferred for longer lesions with an optimal distal re-entry zone, without significant side branches that could be occluded by the technique, or when an initial wire escalation strategy failed. Wire-based anterograde dissection/re-entry was also used successfully when an initial attempt at crossing from a “true-to-true” approach failed. Such a strategy involves the use of a microcatheter delivered on a knuckled polymer-jacketed wire advanced into the subintimal dissection plane, with subsequent re-entry into the true distal lumen using a stiff tapered guidewire or a knuckled guidewire. A Stingray system will be used to cross from the false lumen to the true lumen, the so-called hybrid procedure, rapidly switching from one approach to another when the initial strategy attempted is failing.

For the main analysis, the investigators consider that the lesion is crossed with dissection/re-entry when (1) a wire-based antegrade dissection was performed followed by re-entry into the true distal lumen with a straight or knuckled wire/CrossBoss, (2) A Stingray system was used to cross from the false lumen to the true lumen, and (3) when a reverse-controlled antegrade and retrograde re-entry technique is used to cross the CTO segment. Other CTO crossing techniques were considered “intraplaque,” “true-to-true,” or wire escalation techniques(as **figure 1**).

3. Intervention Procedures

- ① All patients receive optimal intravenous hydration the days before and after PCI.
- ② Patients receive an initial bolus of intravenous unfractionated heparin (100 IU/kg). The activated clotting time is monitored every 30 min to determine if an additional bolus of unfractionated heparin is necessary to maintain an activated clotting time >250s. Upstream use of glycoprotein IIb/IIIa inhibitor therapy or bivalirudin is avoided.
- ③ All procedures are performed via the radial or/and femoral route, with double coronary cannulation and contralateral selective injection. Seven-French guiding catheters are used in most cases.
- ④ All operators have received proctoring in AWE, antegrade dissection re-entry (ADR), retrograde wire escalation (RWE) and retrograde dissection re-entry (RDR) approaches used in the hybrid algorithm. And operators have performed a career minimum of 300 CTO cases.
- ⑤ To adjust the patients number in intimal stents group and subintimal stents group with either the antegrade or the retrograde approach, wire escalation technique was made as the first choice in all patients, if failed, to choose which CTO revascularization strategy is left to the operator’s discretion (Fig 1). The selection of the optimal initial CTO crossing strategy is dependent on the anatomy of the coronary vessels. Four angiographic characteristics are used to make the decision (Fig. 1): (a) lesion length (lesions ≥ 20 mm in length tend to have lower success rates and longer procedure times using standard antegrade wire escalation); (b) proximal cap location and morphology; (c) size, quality (i.e. vessel size and presence of luminal stenoses

and/or calcification) and presence of side branches of the target coronary vessel at the distal cap; and (d) size and suitability of collateral circulation for the retrograde technique. Several guidewire strategies are used, including the single-wire technique, the parallel-wires technique, the intravascular ultrasound–guided wiring technique, and retrograde wiring through collateral vessels, such as simple retrograde wiring, kissing wires, the knuckle technique, and the CART and reverse CART techniques, as previously described.

⑥ The number and type of approaches (AWE/ADR/RDR/RWE) required to cross the CTO segment are recorded. Wire crossing time is from insertion of the guidewire into either the target vessel or retrograde donor vessel to when the wire successfully crossed the CTO segment and re-entered the true lumen.

⑦ The occluded segment is stented with second generation DESs(XIENCE, Abbott) (if no contraindication for prolonged dual antiplatelet therapy) and post-dilation performed to optimize stent expansion and apposition as needed.

⑧ In this study, by evaluating CTO lesions in the pre-stenting and post-PCI period, the investigators seek to identify the predictors of ISR. The standard restenosis scores (R-scores) related six factors including: A: the number of stent ($n < 2$ 0score; $2 > n < 4$ 1score; $n > 4$ 2score); B: stent length ($< 35\text{mm}$ 0score; $36\text{-}70\text{mm}$ 1score; $> 71\text{mm}$ 2 score); C: lumen dissection length ($< 20\text{mm}$ 0score; $21\text{-}30\text{mm}$ 1score; $> 31\text{mm}$ 2score) ; D: calcification (mild 1score; severe 2score; E: lumen area ($< 5\text{mm}^2$ 3score; $5\text{-}7\text{mm}^2$ 2score; $> 7\text{mm}^2$ 1score) and F: angulation slight ($> 45^\circ$ single bend 1score), moderate (2 bends $> 45^\circ$ or 1 bend $> 90^\circ$ 2 score) or severe (2bends $> 90^\circ$ or 1bend $> 120^\circ$ 3score). Additionally, the investigators will utilize IVUS as a tool to evaluate predictor factors to obtain in-depth analyses of the lesions.

[figure not shown]

Figure 1: CTO PCI techniques in trial

4. Statistical analysis

Discrete data are summarized as frequencies and continuous data as mean \pm SD or median and interquartile range. Chi-square test or Fisher exact test analyses were used for comparison of categorical variables. The multivariable analysis to evaluate the independent contribution of clinical, angiographic, and procedural variables to re-occlusion and in-segment restenosis was performed by forward stepwise logistic regression analysis. Cumulative survival analyses were performed using the Kaplan-Meier method, and the difference between curves was assessed by log-rank test. A multivariable analysis by forward stepwise Cox proportional hazards model was performed to evaluate the independent predictors of death, myocardial infarction, and target CTO vessel revascularization. Odds ratios (ORs), hazards ratios (HRs), and their 95% confidence intervals (CIs) were calculated.

All tests were 2-tailed. A p value <0.05 was considered significant. Analyses

were performed using the software package SPSS (version 11.5, SPSS Inc., Chicago, Illinois).

REFERENCE

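### No planned analysis accounts for centre in a nonrandomized ten-centre comparison, so centre differences in technique use and restenosis could bias the technique comparison or inflate its false-positive rate, by an unknown amount

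*Combined protocol and SAP*

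**What the plan says.** Methods, section 1, item 1 describes a "prospective, exploratory, nonrandomized, multicenter trial". Item 2 states that "300 CTO cases, to which PCI will be attempted, are prospectively enrolled", and places this enrolment "in the CTO registries of ten centers". The introduction gives comparing the effect of dissection/re-entry on outcomes as a purpose of the study.

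Section 3, item 5 sets out how technique is chosen. Wiring is tried first in every patient. Should it fail, the item says: "to choose which CTO revascularization strategy is left to the operator". The same item says that anatomy determines the initial strategy and lists four angiographic characteristics.

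Section 4 is the whole statistical plan. For group comparisons, "Chi-square test or Fisher exact test analyses were used for comparison of categorical variables". It adds forward stepwise logistic regression for re-occlusion and restenosis (on clinical, angiographic and procedural variables), Kaplan-Meier curves with a log-rank test, and forward stepwise Cox regression. Tests are two-sided at 0.05. Neither centre nor operator appears as a stratum, covariate, random effect, frailty or cluster adjustment.

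**The concern.** Centre confounds a nonrandomized comparison if it is linked both to technique and to outcome. The protocol leaves both links open.

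- **Centre and technique.** Section 3, item 5 gives no criterion for when wire escalation has failed, and the next step is the operator's choice. Section 2, item 9 also describes device-based dissection/re-entry as preferred for some longer lesions. That must be reconciled with the wire-first statement, because as written the two can be read differently at different sites.
- **Centre and restenosis.** Case mix can differ by site. Post-dilation is done as needed (section 3, item 7). Operators enter the outcome data (section 1, item 4) and no core laboratory is named. The endpoint is a cut at 50% narrowing (section 2, item 7), so local reading habits could shift it.

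If centres that use more dissection/re-entry also have higher or lower restenosis, a pooled test attributes part of that difference to technique. With only ten centres, chance alignment alone can push the error rate above its nominal level.

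**Working it through.** **1. The plan's own figure.** Item 2 of section 1 says that "the patients percentage of ADR or RDR strategy application was just only 20-25"% and concludes: "If to get 60 patients for ADR or RDR strategies, the minimum CTO number are 300 patients". Check: 60 / 0.20 = 300, which reproduces the figure; 60 / 0.25 = 240, so the plan uses the lower end of its range. This leaves 300 − 60 = 240 wire-escalation patients. Per centre the average is 300 / 10 = 30 patients, of whom 60 / 10 = 6 have dissection/re-entry. The plan gives no expected restenosis rate, power or centre variation, so there is nothing further to reproduce.

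**2. Mechanism, without simulation (assumed rates).** Five centres (150 patients) use dissection/re-entry in 5% and have 10% restenosis. The other five (150 patients) use it in 35% and have 20% restenosis. Technique has no effect within any centre.

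- Dissection/re-entry: 7.5 + 52.5 = 60 patients; restenosis (7.5 × 0.10 + 52.5 × 0.20) / 60 = 11.25 / 60 = 18.75%.
- Wire escalation: 142.5 + 97.5 = 240 patients; restenosis (142.5 × 0.10 + 97.5 × 0.20) / 240 = 33.75 / 240 = 14.06%.
- Pooled odds ratio: (0.1875 × 0.8594) / (0.1406 × 0.8125) = 1.41, against 1.0 within every centre.

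With use of 10% and 30% the pooled odds ratio is 1.26. With equal use of 20% it is 1.00, so the distortion needs use and restenosis to vary together.

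**3. Simulation.** From the documents: 10 centres, 300 patients, 20% dissection/re-entry, two-sided 0.05. Assumed: 30 patients in every centre, 17% restenosis, no technique effect, and normally distributed centre effects on the log-odds of use and of restenosis, with the SDs and correlation shown. The 20% and 17% are averages over centres. There are 20,000 trials per setting, so the Monte Carlo standard error near 5% is √(0.05 × 0.95 / 20,000) = 0.15 points.

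Notation: in a centre of m patients, n1 have dissection/re-entry and n0 wire escalation, with a and b restenoses and k = a + b. N1, N0, A and B are the totals over centres, and p = (A + B) / 300.

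- Crude chi-square: (A/N1 − B/N0)² / [p(1 − p)(1/N1 + 1/N0)].
- Cochran-Mantel-Haenszel: (Σa − Σn1k/m)² / Σ[n1n0k(m − k) / (m²(m − 1))].

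Both are compared with 3.84.

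| SD restenosis / SD use | Crude, correlation 0 | Crude, correlation 0.5 | Mean spurious difference at 0.5 |
|---|---|---|---|
| 0.3 / 0.5 | 4.9% | 5.8% | 0.9 points |
| 0.5 / 0.8 | 5.8% | 9.1% | 2.3 points |
| 0.7 / 1.0 | 7.3% | 14.8% | 3.6 points |

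At correlation 0 the mean spurious difference is zero. The centre-stratified test stays at 4.7-5.1% throughout. If 20% and 17% are instead the rates in a typical centre, the largest figure is about 16.6%.

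**4. Smaller primary-endpoint sample.** Section 1, item 4 schedules angiography only after successful PCI and without moderate or severe renal insufficiency, so fewer than 300 cases will contribute. With an assumed 22 per centre, the crude rates at correlation 0.5 are 5.8%, 8.2% and 12.8%. The abstract describes the 300 as successfully revascularized, while section 1, item 2 describes them as attempted; these should be reconciled.

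**The case against.** The strongest reply is that nothing in the documents shows centres to differ, and that several features narrow the scope for it. Wiring comes first in all patients, four anatomical characteristics guide strategy, all operators are proctored in all four approaches and have at least 300 career cases, and one stent family is used. The stepwise models may also absorb some centre difference through recorded lesion and stent variables. The study calls itself exploratory. Confounding by lesion anatomy is the more evident bias, because dissection/re-entry follows failed wiring.

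Most of this stands and limits the claim. Three stronger readings are tempting but unsupported:

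- **That operators choose technique freely.** Section 3, item 5 gives discretion only after wire escalation has failed.
- **That the pooled test is known to have an inflated error rate, of 9% or 15% say.** Those figures need a centre-level correlation of 0.5 that the documents do not supply. At zero correlation there is no mean bias and inflation is small.
- **That every planned analysis has been shown to mislead.** Only the crude chi-square test was simulated. Residual centre bias in the logistic, log-rank and Cox analyses has not been quantified.

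The reply does not remove the point. The chi-square and log-rank tests use no covariates, centre is not a named candidate in either model, and stepwise selection need not keep technique or any confounder. Although exploratory, the plan still declares significance at 0.05.

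**Conclusion.** The omission is certain: no analysis in section 4 accounts for centre. The consequence is conditional. Bias requires technique use and restenosis to vary together across centres; some inflation can arise without that correlation if both vary. Under the assumed settings, the crude false-positive rate is about 5-7% at zero correlation and about 6-15% at 0.5, the latter with a spurious difference of about 1-4 points. Small heterogeneity makes almost no difference. The true size cannot be known from the documents. This is a worthwhile correction that ranks below adjustment for lesion anatomy.

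**What to change.** Amend section 4 as follows:

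- Stratify the crude restenosis comparison by centre with a Cochran-Mantel-Haenszel test.
- In the restenosis regression, keep technique in the model regardless of selection, and add a centre random intercept (or condition on centre) alongside the recorded lesion and patient covariates. With about six dissection/re-entry patients per centre on average, this is safer than nine centre indicators in a stepwise model.
- Stratify the log-rank and Cox analyses by centre.
- Report technique share and restenosis by centre, so that readers can see how far they vary together.

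The cost is SAP wording, since each patient's centre is already known. The downside is a small loss of information from centres with few dissection/re-entry cases. If centres do not differ, little is lost: with no centre variation, the crude and stratified tests both reject at about 4.8%. Stratifying by centre leaves confounding by lesion anatomy in place, so covariate adjustment is still needed.

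### The 13-month restenosis call, the primary endpoint, has no stated measuring method, reader or masking to crossing technique, and operators collect and enter the outcome data.

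*Combined protocol and SAP*

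**What the plan says.** All references are to the Combined protocol and SAP.

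- **Endpoint.** Methods 2 (Study endpoints and definitions), item 1: "The primary study endpoint of the protocol is the binary in-stent restenosis of CTO vessels at the scheduled angiographic follow-up at 13 months".
- **Threshold and segment.** Methods 2, item 7: "restenosis is defined as > 50% luminal narrowing at the segment site, including the stent and 5 mm proximal and distal" to the stent edges. No unit (diameter or area), reference vessel or measuring technique is given.
- **Modality.** Methods 1 (Trial overview and study population), item 4: "Compared with CTA, coronary angiography to evaluate restenosis is appropriate in all patients". This settles the type of imaging, not how a percentage is read from it.
- **Data collection.** Methods 1, item 4: "Procedural and outcome data collection will be collected and entered by operators entered into a dedicated database".
- **Percent stenosis elsewhere.** The only method named for a percent stenosis is in Methods 2, item 3, for residual stenosis at the index procedure: "by visual estimation and TIMI flow grade 3 after CTO recanalization". Methods 3 (Intervention Procedures), item 8, assigns intravascular ultrasound to predictor factors, not to the restenosis call.
- **Choice of technique.** Methods 3, item 5, makes wire escalation the first choice for everyone. If it fails, "to choose which CTO revascularization strategy is left to the operator’s discretion".
- **Expectation.** The Introduction raises the possibility that subintimal stenting itself causes restenosis, and then cites limited data in which it did no harm.

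No section mentions a core laboratory, a masked reader, a second reading or adjudication. The one figure not shown is captioned as PCI techniques, so it is unlikely to hold this information.

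**The concern.** A binary call at a 50% cut is most open to judgement in borderline films. The study is nonrandomised and operators know the technique. If the person reading the film also knows it, borderline films may be called differently in the two groups. Because the Introduction points both ways, the drift could create a difference or hide one.

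Such drift sits in the outcome variable. It feeds both the comparison of intimal with subintimal stenting and the stepwise logistic model for restenosis (section 4, Statistical analysis), and adding covariates to that model does not remove it. The missing unit adds a separate ambiguity, because 50% by diameter and 50% by area are different thresholds.

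**Working it through.** **1. The plan's own figure.** Methods 1, item 2, wants 60 dissection/re-entry patients and cites a 20-25% share for those techniques. 60 / 0.20 = 300, which reproduces the stated total; at 25% it would be 60 / 0.25 = 240. The group sizes used below are therefore 60 subintimal and 300 − 60 = 240 intimal. The plan gives no expected restenosis rate, effect size or power, so every rate below is an assumption.

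**2. The missing unit.** For a circular lumen, area varies with the square of diameter. A 50% diameter reduction is a 1 − 0.5² = 75% area reduction. A 50% area reduction is only a 1 − √0.5 ≈ 29% diameter reduction. The same film can be positive on one reading and negative on the other.

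**3. Creating a difference.** Assume that 10-20% of films are borderline and that readers call them positive 30-50 percentage points more often in the subintimal group.

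False difference = borderline share × excess calling: 0.10 × 30 = 3 points, up to 0.20 × 50 = 10 points.

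Assume 15% called restenosed in the intimal group, no true difference, and the shift added to the subintimal group only. Exact binomial enumeration of the uncorrected two-sided chi-square test at 0.05 gives:

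| Called restenosed, subintimal vs intimal | 60 vs 240 films | 48 vs 192 films |
|---|---|---|
| 15% vs 15% | 4.8% | 4.7% |
| 18% vs 15% | 10% | 9% |
| 20% vs 15% | 17% | 15% |
| 21% vs 15% | 22% | 18% |
| 25% vs 15% | 45% | 38% |

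The last column assumes an 80% film yield (0.8 × 60 = 48; 0.8 × 240 = 192). Some loss is built in: Methods 1, item 4, schedules angiography only after successful PCI and without moderate or severe renal insufficiency, while item 2 counts the 300 as attempted cases (the Abstract says successful).

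**4. Hiding a difference.** Observed rate = p × Se + (1 − p) × (1 − Sp), where p is the true rate and Se and Sp are the reader's sensitivity and specificity. Assume true rates of 10% intimal and 25% subintimal, 60 vs 240 films, and lenient reading of the subintimal group:

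- Subintimal, Se 0.80 and Sp 0.98: 0.25 × 0.80 + 0.75 × 0.02 = 21.5%.
- Intimal, Se 0.95 and Sp 0.90: 0.10 × 0.95 + 0.90 × 0.10 = 18.5%.

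By normal approximation the probability of p<0.05 falls from 82% with perfect reading to 9%.

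**5. Equal error in both groups.** With Se = Sp = 0.90 in both groups and no true difference, the false-positive rate stays at 5%. With true rates of 10% and 25%, power falls from 82% to 54%. Masking therefore addresses the false-positive risk; better measurement addresses the loss of power.

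**The case against.** Four objections have weight.

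**The text does not say who reads the film.** A reader might infer that each operator judges by eye whether his or her own stent has restenosed. The documents do not support that. They say that operators collect and enter outcome data; they do not say that the treating operator reads the 13-month film, and they name visual estimation only for the index result. Nor is the technique freely chosen, since wire escalation comes first. What stands is that reader, method and masking are unstated and nothing excludes the treating operator.

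**The damage may be repairable.** A reader might infer that drift, once in the data, is permanent. If the films are kept, a later masked re-read could recover the endpoint. The plan makes no provision for one, so the point remains worth settling beforehand.

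**The size is assumed.** Neither the borderline share nor the excess calling comes from the documents. A larger false-positive rate, about 55%, appears only if the 10-point shift is split around 15% (20% vs 10%), which also requires under-calling in the intimal group.

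**The study is exploratory and nonrandomised.** Failed wire escalation steers patients into the subintimal group, so confounding limits causal conclusions even with perfect reading. That is true, but the plan still tests at p<0.05, and confounding does not excuse an avoidable second source of bias.

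A related worry is that edge narrowing already present after the procedure could be counted as restenosis. This is thin: only successful cases, with residual stenosis below 30%, go on to angiography, and the documents give no frequency for it.

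**Conclusion.** The concern holds as a gap in how the primary endpoint is ascertained. Threshold, segment and modality are stated; unit, quantification, reader and masking are not, and the data-collection sentence leaves the treating operator free to make the call. The documents show that technique-dependent reading is possible in either direction. They do not show that it occurred.

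The best available size is illustrative: with 3 to 10 points of over-calling in one group, the false-positive rate rises from about 5% to about 10-45% with all 300 films, or about 9-38% at an 80% yield. Those figures rest on the assumed 15% rate, the assumed drift and the 60:240 split. The change should be made: it is cheap and protects the primary comparison.

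**What to change.** Make two changes of wording.

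1. **Methods 2, item 7.** Define restenosis as more than 50% *diameter* stenosis by quantitative coronary angiography on the recorded film, over the stent and 5 mm beyond each edge.
2. **Methods 1, item 4.** Have each 13-month film read for the primary endpoint by an existing investigator at another of the ten centres, without the crossing-technique field, in place of the treating operator. Operators continue to enter procedural data.

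Measuring the same segment by the same method on the final index film is an optional addition, and would answer the edge-narrowing worry.

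The cost is transfer of de-identified films between centres and offline measurement time, more if index films are included. No new reader or patient procedure is needed, because the angiograms are already scheduled. Masking will be partial: stent length or appearance may hint at the technique, since Methods 2, item 9, prefers device-based dissection/re-entry for longer lesions. Taking the call away from the treating operator and measuring it quantitatively still narrows the room for discretion.
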